Protocol # 64989743

Principal Investigator: [name], D.O., FAOCO

Sub investigator: N/A

Site: Private Practice and Research Center

Surgery Center: Tinley Woods Surgery Center

Measurements: [name] Eye Care @ Laser and Cataract Institute, [name]

Post Operative visits: [name] Eye Care @ Laser and Cataract Institute, [name] and [name]

Background: Cataract surgery is projected to be the most commonly performed surgical procedure over the next 10-15 years. Patient expectations of good visual outcomes have risen with the increase in the advancing technology being offered. Cataract surgeons are in need of a clear and consistent process in order to deliver the best possible outcomes with the least amount of error.

Rationale: Biometry data and accurate intraocular lens (IOL) calculations are arguably the most important steps in achieving the desired refractive outcomes. There is limited evidence comparing the two biometers, Zeiss IOL Master 700 to Alcons Argos.

Randomized Observational Prospective Trial:

Hypothesis: The Alcon Argos Biometer's measurements, when used in conjunction with the Barrett Universal II formula, will provide statistically non-inferior outcomes (Mean Absolute Prediction Error of Predicted Spherical Equivalents), when compared to the IOL Master 700 utilizing the (PCA) with the Barrett Universal II (TK) Formula for IOL power calculations.

Primary Objective: To assess if the Alcon Argos Biometer utilizing the Barrett Universal II formula for IOL calculations can give a non-inferior outcome when compared to the Zeiss IOL master 700 utilizing the (PCA) with the Barrett Universal II (TK) formula, when comparing the (mean absolute prediction error of the predicted target spherical equivalencies).

Primary End Point: Mean Absolute Prediction Error (MAPE) of predicted spherical equivalents per biometer. (The absolute value of the difference between the Predicted Post-OP MRSE to the Actual Achieved Post-OP MRSE for the IOL implanted). 2 biometers (Argos and IOL Master 700). Primary End Point (MAPE) will be based on the manifest refraction SE obtained at the postoperative visit day 30 (- 2/+14 days).

Secondary End Points:

a) Percentage of eyes with an Absolute Prediction Error of Predicted SE < or = to (0.5D) with Argos vs IOL Master 700

Protocol # 64989743

b) Median Absolute Prediction Error of Predicted Spherical Equivalents per biometer

(The absolute value of the difference between the Predicted Post Op MRSE to the actual achieved Post Op MRSE for the IOL implanted) Secondary end points will be based on manifest refraction SE obtained at the postoperative visit day 30 (-2/+14 days)

Exploratory End Points:

a) Percentage of eyes with an Absolute Prediction Error of Predicted SE < or = to (0.25D) with Argos vs IOL Master 700

Safety: All subjects enrolled in the study will be evaluated for safety.

Proposed Method: To enroll approximately 80 patients, 80 right eyes in a randomized observational prospective study over the course of approximately 4 months (8.5 month estimated total study time), randomizing the patients into one of two arms.

Two Arms: All scanned by the same technician (Over 2000 scans a year experience)

A. ARGOS, IOL Master 700, 40 patients, 40 right eyes

B. IOL Master 700, ARGOS, 40 patients, 40 right eyes

Randomization of the actual order for biometry measurements will occur utilizing a randomization program, with blocking on every 2 or 4 subjects.

Rationale: Two arms ensure we eliminate dry eye or fatigue bias for each biometer reading by randomizing the order of the preoperative biometry measurements. In between measurements patient will take a timed 2 min break. No drops will be given prior to measurements, no physical contact with the eye will occur prior to any measurements. This will allow for the most accurate keratometry readings.

Barrett Universal Formula II "K" and (TK) are now considered the gold standard in biometry formulas.

The Barrett Universal II Formula "K" Is available on both biometers, while the Barrett Universal II (TK) is only available on the Zeiss IOL Master 700 biometer.

Surgeon will have access to all biometry readings prior to surgery and at the time of surgery. Surgeon will make the lens selection by choosing the IOL (Intraocular lens) power closest to plano for all biometers involved. If the two IOL diopter powers are not in consensus, the surgeon will utilize the Argos Biometer for the selection.

We will utilize the Barrett Universal II "K" formula for the Argos, and the Barrett Universal II (TK) for the IOL Master 700 to compare the mean absolute prediction error for the predicted spherical equivalents by back calculating.

Utilizing the Barrett Universal II (TK) (Anterior and Posterior corneal measurements) available only on the IOL Master 700 and comparing it to the Barrett Universal II "K" on the Alcon Argos biometer will allow us to assess if K measurements give non inferior outcomes to the TK Formula.

The Barrett Universal 2 formula uses a theoretical model eye in which anterior chamber depth (ACD) is related to axial length (AL) and keratometry. A relationship between the A-constant and a "lens factor" is also used to determine ACD.¹ The important difference between

Protocol # 64989743

the Barrett formula and other formulas is that the location of the principle plane of refraction of the IOL is retained as a relevant variable in the formula. (1)

1. An improved universal theoretical formula for intraocular lens power prediction. Barrett GD. J Cataract Refract Surg. 1993 Nov;19(6):713-20.

Surgery: Surgery will be performed by 1 surgeon, who routinely performs over 20-25 cases weekly. Optimized lens settings will be used for each biometer.

Corneal Incision size: 2.4 mm Alcon Dual Bevel Blade (Temporal)

Capsulorhexis: Intended size of 4.8mm to 5.2 mm

Phaco: Alcon Centurion

Lens: Alcon IQ Acrysof SN60WF only

Complications: All subjects with any surgical complications will be excluded.

Exclusion Criteria:

Axial Length < 22.00 and > 26.00

Corneal Astigmatism > +1.00 Diopters

CCTS: < 490 and > 600

Prior Refractive Surgery: RK, PRK, LASIK, INTACTS

History of contact lens use: Soft lenses within 2 months of surgery, RGP within 60 months of surgery

Corneal Disease: Keratoconus, Corneal Dystrophies, Any prior corneal Surgery, Prior infections

Retinal Disease: Macular Pathology, CSCR, CME, Macular Degeneration, Drusen, Retinal Detachment, TPPV, SB, prior IVT, Prior PRP or Focal Laser, Diabetic Retinopathy

History of Uveitis

POAG: Undergoing any concomitant MIGS procedure- iStent, Omni, iTrack, Hydrus, etc

Enrollment in any prior clinical trial within 2 years

Systemic Disease that in the investigator's opinion may affect outcome

Currently Pregnant or Breastfeeding

Severe Dry Eye

Tear Osmolarity > 320mOsms/L (Moderate)

Any Surgical Complication(s)

IOL implanted outside of the capsular bag /capsular damage /weakness /CTR placement

Protocol # 64989743

Inclusion Criteria:

Age: 50-85 years old

Clinically Significant Cataracts that interfere with daily activities

Patient is able to understand and able to consent to informed consent

Patient is able to come to all postoperative visits and agrees to follow up at 30 days -2/+14 days

Patient undergoing cataract surgery, with implantation of the Alcon SN60WF lens in the capsular bag.

Study Visit Time Line:

Visit 1: Screening and initial testing. Initiate dry eye protocol on all subjects

Dry Eye Protocol: Systane Hydration PF drops (or equivalent) 4 x daily and Warm Packs 10 mins nightly for 14 days (+ 5 days maximum).

Visit 2: Dry eye evaluation to occur at day 14 or greater (+ 5 days maximum), randomization for the order (Argos then 700 or 700 then Argos) of bilateral biometry measurements, consents, and study enrollment.

After dry eye protocol, subjects with (Tear Osmolarity > 320mOms/L) will be excluded from the study.

All enrolled subjects will continue to using Systane Hydration PF drop (or equivalent) 4 x a day for the entire duration of the study.

Subjects will discontinue nightly warm packs the night of surgery.

(To minimize the risk of pressure on the eye and potential risk of post operative infection).

Visit 3: Surgery right eye

Visit 4: Post Operative Day 1 right eye

Visit 5: Post Operative Day 6-14 right eye

Visit 6: Post Operative Day 30 (-2/+14) final manifest refraction right eye

The same Optometrist will perform all refractions on all subjects and will be masked to all biometry data.

Surgeon will be masked to all post-operative manifest refraction results until after study conclusion.

Initial Screening Testing Visit to include: Best Corrected Distance Visual Acuity, Auto Refraction, Manifest Refraction, confrontational fields, pupil reflexes, IOP, slit lamp exam anterior and posterior chamber, Tear Osmolarity, Pachymetry, screening for inclusion and exclusion criteria.

Post Op visits to include: Visual Acuity, IOP, Slit Lamp, final postoperative refraction at visit number 6

Study Estimated Time for Completion:

8.5 Months: After fully executed contract, encompassing first patient first visit to last patient last visit, plus full analysis, and final report / draft manuscript.

Protocol # 64989743

Contract Review: 1 month

IRB: 1 month

Enrollment: 4 Months

8 weeks to measure, 2 weeks of dry eye treatment, 4-6 Week for surgery completion, 4 weeks postoperative final visit -2 +/14 days

Data Collection: 30 Days (-2/+14 days)

Data Analysis: 1 Month

Final Report/Draft Manuscript with safety information: 1 Month

Planned Presentations:

ASCRS Interim Data 2022 and/or AAO Full Data 2022

IAO/COS Illinois Academy of Ophthalmology, Chicago Ophthalmic Society (if not restricted) and/ or

AOCOO-HNS: American Osteopathic College of Ophthalmology- Annual meeting (if not restricted)

Planned Publication:

Peer Reviewed Journal: ASCRS- Journal of Cataract and Refractive Surgery or

AAO- Journal of Ophthalmology

Protocol # 64989743

Sample size and statistical analysis:

For this test, a sample size of approximately 70 will provide acceptable power. Up to 10 more subjects will be enrolled to account for dropouts.

The endpoint is based on the absolute deviation from target MRSE measured by two biometers in the same subject. The difference is calculated for each subject where the Alcon biometer absolute error is subtracted from the XYZ biometer absolute error. A value of zero will reflect no difference, where a negative difference indicates that the Alcon biometer has greater error.

We expect the difference to be zero, however, for safety, knowing that the difference can fluctuate around zero, we set this at -1/20 D. In other words, we assume that the Alcon will, on average, have 0.05D more absolute error.

We set power at 90%. We use a one-tailed alpha of 0.025. The standard deviation if the difference in the two biometers is assumed to be 0.5 D and the NI Delta is set at 0.25 D. These settings and assumptions result in a required sample size of 68 subjects. SAS proc power output is provided:

Fixed Scenario Elements

Distribution	Normal
Method	Exact
Lower Equivalence Bound	-0.25
Upper Equivalence Bound	9999
Alpha	0.025
Mean	-0.05
Standard Deviation	0.5
Nominal Power	0.9

Computed N Total

Actual	N
Power	Total
0.902	68

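### The Argos-K versus IOL Master 700-TK comparison cannot show whether K is non-inferior to TK, because the device changes together with the corneal input

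*Combined protocol and SAP*

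**What the plan says.** The Hypothesis and Primary Objective set Argos with Barrett Universal II against IOL Master 700 with Barrett Universal II (TK). The endpoint is the mean absolute prediction error of the spherical equivalent. Proposed Method confirms the two cells: the K "formula for the Argos, and the Barrett Universal II (TK) for the IOL Master 700 to compare the mean absolute prediction error", with predictions back-calculated for the implanted lens. Every eye is measured on both devices, and only the scan order is randomized.

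The Rationale then takes a further step and says that this same comparison "will allow us to assess if K measurements give non inferior outcomes to the TK Formula".

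Three other statements bear on that step:

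- On formula availability, K "Is available on both biometers, while the Barrett Universal II (TK) is only available on the Zeiss IOL Master 700 biometer".
- On lens settings, the Surgery section says "Optimized lens settings will be used for each biometer".
- On the formula's other inputs, the Rationale explains that "anterior chamber depth (ACD) is related to axial length (AL) and keratometry".

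No endpoint or analysis uses Barrett K on the IOL Master 700.

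**The concern.** Between the two cells the device changes, the corneal input changes (K to TK), and the lens settings are tuned to each biometer. The device matters in its own right because it supplies the axial length and keratometry that the formula uses. One paired difference cannot be divided among these sources. Randomizing scan order balances order and fatigue effects but leaves K tied to the Argos and TK to the 700 in every eye. A larger sample would not help, because the problem is identification and not precision.

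At stake is the wording of the conclusion. If the primary test passes and the report repeats the Rationale, it will claim that K is non-inferior to TK without evidence for it. If the test fails because of the device or the lens settings, K could wrongly be blamed.

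**Working it through.** **Inputs.** From Sample size and statistical analysis: paired difference within subject, one-sided alpha 0.025, assumed mean -0.05 D (negative means Argos worse), and "the difference in the two biometers is assumed to be 0.5 D and the NI Delta is set at 0.25 D", where the first figure is the standard deviation. Stated result: N = 68, power 0.902.

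**Reproducing the plan.** Paired non-inferiority t-test with noncentral t:

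- ncp = (mean + margin) / (SD/√n) = 0.20 / (0.5/√68) = 3.30, with 67 df.
- Power is 0.9016 at n = 68 and 0.897 at n = 67, so N = 68 and 0.902 reproduce.
- 95% CI half-width = 1.996 × 0.5/√68 = 0.121 D.
- The test passes when the observed mean exceeds -0.25 + 0.121 = -0.129 D.

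**Decomposition.** Write |e(·)| for the absolute prediction error of one eye. In the plan's sign:

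|e(700-TK)| − |e(Argos-K)| = [|e(700-K)| − |e(Argos-K)|] + [|e(700-TK)| − |e(700-K)|]

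The first bracket is device plus lens settings. The second is corneal input, plus any difference in settings between K and TK on the 700. This is an identity and needs no model. The plan observes only the left side, because 700-K is never computed.

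**What a pass says about K.** The package mean equals the device-plus-settings advantage minus the K deficit. The component values below are assumed; SD is held at 0.5 D and n at 68.

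| K deficit (D) | Device-plus-settings advantage (D) | Package mean (D) | P(pass) |
|---|---|---|---|
| 0 | -0.05 | -0.05 | 90.2% |
| 0.25 | 0 | -0.25 | 2.5% |
| 0.25 | 0.05 | -0.20 | 12.6% |
| 0.25 | 0.10 | -0.15 | 36.9% |
| 0.25 | 0.15 | -0.10 | 68.4% |
| 0.25 | 0.20 | -0.05 | 90.2% |
| 0 | -0.20 | -0.20 | 12.6% |

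The first and sixth rows give the same package mean and the same chance of passing, yet opposite answers about K. A valid K-versus-TK test would pass in 2.5% of trials at a deficit equal to the margin. The last row is the reverse error: K equals TK, but the test usually fails.

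**What a 700-K prediction would give.** The documents state no SD for 700-K versus 700-TK. Over an assumed range at n = 68:

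| SD (D) | 95% CI half-width (D) | Power, margin 0.25 D, mean -0.05 D |
|---|---|---|
| 0.1 | 0.024 | >0.999 |
| 0.2 | 0.048 | >0.999 |
| 0.3 | 0.073 | >0.999 |
| 0.4 | 0.097 | 0.982 |
| 0.5 | 0.121 | 0.902 |

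**The case against.** The strongest reply is that the operative plan never tests K against TK. The hypothesis, objective, endpoints and sample size are all framed as biometer against biometer or package against package. The sentence at issue names both devices before it reaches its conclusion, so it can be read as shorthand for the Argos-K cell. Harm arises only if a report repeats that sentence in place of the primary objective. The 90.2% figure also needs a 0.20 D offsetting advantage that nothing in the documents supports; at 0.05 D or less the pass rate is at most 12.6%. Finally, the plan does not say how the lens settings were optimized, or whether they differ between devices or between K and TK.

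Much of this stands. The primary analysis needs no change, the splits cannot show how likely a wrong inference is, and a difference in lens settings is a reasonable reading of the text but not an established fact. None of it rescues the sentence, whose conclusion is literally about K measurements and the TK formula. Device and corneal input alone are enough to confound that conclusion, whatever the settings are. Since publication in a peer-reviewed journal is planned, the wording matters.

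**Conclusion.** The concern holds and should be fixed. The planned contrast supports a claim about Argos with Barrett K against IOL Master 700 with Barrett TK, and nothing narrower. The test controls its 2.5% error for the package difference only. For K versus TK at a 0.25 D deficit, the chance of a pass runs from 2.5% to 90.2% as the assumed device-plus-settings advantage goes from 0 to 0.20 D.

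The identification argument rests only on the plan's pairing of formula with device. The percentages rest on the plan's SD, margin and N together with assumed component values. The sample size and the primary package conclusion are sound on this point.

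**What to change.** 1. Keep the primary contrast, margin and alpha, and report the result as a device-plus-formula package.
2. Reword the Rationale sentence, for example: *The comparison tests non-inferiority of Argos with Barrett K to IOL Master 700 with Barrett TK; effects of corneal input, device and lens settings are not separated.* This alone removes the unsupported claim, at no cost.
3. If a K-versus-TK statement is wanted, also back-calculate the 700-K prediction for the implanted lens. First confirm that the 700 acquisition yields both K and TK outputs, which is inferred from the availability statement. State the 700-K lens settings in advance. If they differ from those for 700-TK, label the contrast as corneal input plus its lens settings.
4. Pre-specify two supportive paired contrasts with 95% CIs, outside the primary alpha: 700-K versus 700-TK, and Argos-K versus 700-K.
5. Call 700-K *non-inferior* to 700-TK only against a margin stated and justified in advance, and test it only after the primary passes. The existing 0.25 D was set for the two-biometer difference and could be lenient here if the within-device SD is small. Otherwise report the estimate and CI only.

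Steps 3 to 5 cost one extra back-calculation per eye and two supportive analyses. They need no extra subjects, and no extra visit or scan if the 700 gives both outputs. The choice should be made before results are unmasked.

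### Does excluding subjects for surgical complications, known only after enrolment, take them out of the safety evaluation or harm the primary comparison?

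*Combined protocol and SAP*

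**What the plan says.** The Complications line of the Surgery section reads: "Complications: All subjects with any surgical complications will be excluded". The Exclusion Criteria list surgical complications again and add "IOL implanted outside of the capsular bag /capsular damage /weakness /CTR placement". The Inclusion Criteria contain a matching item: "Patient undergoing cataract surgery, with implantation of the Alcon SN60WF lens in the capsular bag".

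Under Study Visit Time Line, Visit 2 covers randomization of the order "of bilateral biometry measurements, consents, and study enrollment". The next step is "Visit 3: Surgery right eye", followed by postoperative visits on day 1, on days 6 to 14 and around day 30. The Safety statement reads: "All subjects enrolled in the study will be evaluated for safety". The timetable for completion includes safety information in the final report.

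**The concern.** Eligibility criteria should be decidable before a subject is enrolled. A complication, the final lens position and the use of a capsular tension ring become known in the operating room, after enrolment and randomization, so these items work as removals after enrolment. The plan does not say whether they remove the subject from the study or only the eye from the refractive analysis, and it names no analysis sets.

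On the study-level reading, the rule collides with the Safety statement, and the subjects with the most to contribute to a safety report would drop out of it. Removals after randomization also raise the usual questions about selection and loss of power. The situation would probably arise: at assumed complication rates of 1%, 2% and 5%, the chance of at least one case among 80 subjects is 55%, 80% and 98%.

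**Working it through.** **Scope of the exclusion**

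1. The Safety statement applies to all enrolled subjects. Enrolment is at Visit 2 and surgery at Visit 3, so a subject with a surgical complication is already enrolled and already covered.
2. The Complications line gives no object for the exclusion. For tear osmolarity the plan does give one: such subjects "will be excluded from the study". That rule is applied after the dry eye treatment, at the visit where consent and enrolment take place. It is a screen and says nothing about subjects already operated on.
3. No text cancels the three postoperative visits after a complication.
4. Exclusion from the refractive comparison satisfies every statement. Exclusion from the study contradicts the Safety statement. The consistent reading is the first.

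**Bias in the primary comparison**

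Each biometer's error is the absolute difference between its predicted refraction and the single achieved refraction of that eye. Omitting an eye removes both errors together. Randomization governs only the order of the two scans. Intraoperative events are known before the day-30 refraction, and the surgeon is masked to postoperative refractions until the study has ended. The result therefore cannot drive the omission.

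**Power**

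Inputs from Sample size and statistical analysis: assumed mean difference -0.05 D, margin -0.25 D, SD of the paired difference 0.5 D, one-sided alpha 0.025, target power 0.90. About 80 subjects are enrolled, of whom up to 10 allow for dropouts.

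- Distance from the margin: -0.05 - (-0.25) = 0.20 D.
- Noncentrality: (0.20 / 0.5) × √n = 0.4√n.
- Power: 1 - F(t(0.975, n - 1)), where F is the noncentral t distribution function with n - 1 degrees of freedom.
- Plan's own figure: n = 68 gives 0.902 and n = 67 gives 0.897, so the stated 68 is reproduced.

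The complication rate p is an assumption, shown over 1% to 5%. Expected cases are 80p, and the chance of at least one is 1 - (1 - p)^80. Power uses the number of eyes rounded down.

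| Assumed p | Expected cases | Chance of at least one | Eyes left, no dropouts | Power | Eyes left, 10 dropouts | Power |
|---|---|---|---|---|---|---|
| 1% | 0.8 | 0.552 | 79.2 | 0.940 | 69.2 | 0.906 |
| 2% | 1.6 | 0.801 | 78.4 | 0.937 | 68.4 | 0.902 |
| 5% | 4.0 | 0.983 | 76.0 | 0.931 | 66.0 | 0.893 |

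Enrolment of 80 tolerates 80 - 68 = 12 losses of any kind (12 / 80 = 15.0%) before fewer than 68 eyes remain.

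**The case for a change.** The strongest argument for a change is that the Safety statement and the exclusion rule are never linked, and the rule carries no exception for safety. Someone preparing the report could take an exclusion criterion at face value and leave these subjects out. The phrase "any surgical complications" is also undefined, so the decision to omit an eye is made after surgery without a written standard. The extra 10 subjects are described as cover for dropouts only, so surgical omissions come on top. Since a clarification would cost only a line of wording, why not ask for it?

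Part of this stands. The timing mismatch is real: most of these items cannot be screened for at Visit 2. Capsular weakness may sometimes be known beforehand, and the in-the-bag inclusion item can be read as describing the planned operation. The scope is unstated, and with full dropout at an assumed 5% complication rate, power dips just below 90%.

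The consequence does not stand. Leaving these subjects out of the safety report would mean setting aside an explicit statement about all enrolled subjects in favour of an unqualified verb. The 55% to 98% figures give the chance that a complication occurs, not the chance that it goes unreported. The undefined term cannot favour one biometer systematically, because both errors leave with the eye and the refraction is not yet known.

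**Conclusion.** No change to the plan is needed. Followed as written, it gives a within-eye comparison in uncomplicated, in-the-bag eyes and a safety evaluation of all enrolled subjects. Placing intraoperative events under eligibility is a loose way of describing the refractive analysis population. Writing down the scope would be tidy, but it would not alter the primary comparison, the sample size of 68 or the visits.

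The effect on power is small. At assumed complication rates of 1% to 5%, power is 0.940 to 0.931 without dropouts and 0.906 to 0.893 with all 10 allowed dropouts, against 0.902 at the planned 68. This rests on the plan's own SD and mean difference and on the assumed rates. The safety conclusion rests on taking the all-enrolled statement at its word.

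### Do the optional interim presentation and the undated lens settings leave room to re-tune one biometer after refractions are seen?

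*Combined protocol and SAP*

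**What the plan says.** Planned Presentations lists several optional meetings, one of them as "ASCRS Interim Data 2022 and/or AAO Full Data 2022". It does not say what the interim would contain, its cut-off, who would prepare it or who would see it. The timeline section has a single analysis stage ("plus full analysis, and final report / draft manuscript"), and the statistical section describes no interim look.

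Two masking rules stand in Study Visit Time Line:
- "Surgeon will be masked to all post-operative manifest refraction results until after study conclusion".
- "The same Optometrist will perform all refractions on all subjects and will be masked to all biometry data".

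The Surgery section states "Surgery will be performed by 1 surgeon" and "Optimized lens settings will be used for each biometer". Proposed Method says that Barrett K on Argos and Barrett TK on the IOL Master 700 are used "to compare the mean absolute prediction error for the predicted spherical equivalents by back calculating". It also says that the surgeon has all biometry readings before surgery and chooses the lens from the powers that both devices give.

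In the sample-size section the endpoint is a within-subject difference in absolute error, and "the NI Delta is set at 0.25 D".

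**The concern.** Every efficacy endpoint uses the day-30 refraction. An interim with efficacy content would therefore need the data that the masking rule withholds, and with one surgeon and no sub-investigator it is natural to ask whether that surgeon would see it.

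The weightier worry is the lens settings. They enter the predicted spherical equivalent, and so one side of every prediction error. The paired design, the common implanted lens, the common refraction and the masked optometrist all protect the achieved refraction. None of them protects the prediction. If someone adjusted one device's settings after seeing refractions, only that device's errors would shrink, and the primary paired difference would move with them. This could happen at the final back-calculation even if no interim were presented. At stake would be a non-inferiority claim owed partly to the adjustment.

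**Working it through.** **1. The plan's own figure.** The inputs from the sample-size section are mean difference −0.05 D, bound −0.25 D, paired SD 0.5 D, one-sided alpha 0.025 and power 90%. For the exact paired t-test, power is P(T > t(0.975; n−1)), where T is noncentral t with noncentrality (mean + 0.25)/(SD/√n). At n = 67 power is 0.897 and at n = 68 it is 0.902. The printed N of 68 and power of 0.902 reproduce.

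**2. How far re-tuning one device could move its mean absolute error.** The documents give no offset and no prediction-error SD, so both are assumed. For normal errors with offset μ and SD s:

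MAE(μ, s) = s√(2/π)·exp(−μ²/2s²) + μ[1 − 2Φ(−μ/s)]

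The gain from removing the offset is MAE(μ, s) − MAE(0, s):

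| Offset | s = 0.3 | s = 0.4 | s = 0.5 | Share of 0.25 D margin |
|---|---|---|---|---|
| 0.1 D | 0.0132 | 0.0099 | 0.0080 | 3.2–5.3% |
| 0.2 D | 0.0513 | 0.0391 | 0.0315 | 12.6–20.5% |
| 0.3 D | 0.1106 | 0.0858 | 0.0697 | 27.9–44.2% |

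If there is no true offset (s = 0.4, n = 68, simulated), re-centring on the trial's own data gains only about 0.002 to 0.004 D. That is at most 0.004/0.25 = 1.6% of the margin.

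**3. Effect on the test at the planned difference.** With N = 68 and paired SD 0.5 D, I shift the mean from −0.05 D by the s = 0.5 gains. Power goes from 90.2% to 92.2%, 96.4% and 99.2%.

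**4. Effect at the margin, and whether that case is possible.** The same shifts from a true difference of −0.25 D move the chance of a non-inferiority claim from 2.5% to 3.4%, 7.4% and 20.4%. These inputs do not fit together. Suppose Argos has s = 0.5 and is 0.25 D worse, and the IOL Master errors are normal and unbiased:

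- Argos MAE is 0.4069, 0.4304 or 0.4687 D, so the IOL Master MAE is 0.157, 0.180 or 0.219 D (subtract 0.25).
- The SD of the Argos absolute error is √(s² + μ² − MAE²) = 0.307, 0.324 or 0.347 D.
- The IOL Master error SD is MAE/√(2/π) = 0.197, 0.226 or 0.274 D. The SD of its absolute error is that times √(1 − 2/π), or 0.119, 0.136 or 0.165 D.
- The largest possible paired SD, under perfect negative correlation, is the sum: 0.426, 0.460 or 0.512 D.

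The 0.5 D used exceeds the first two limits, and reaching it in the third needs almost perfectly opposed errors in the same eye. So 3.4% and 7.4% cannot occur under these assumptions. This does not make the risk smaller: at the largest feasible SDs of 0.426 and 0.460 D the same shifts give 3.5% and 8.0%.

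**5. The passages side by side.** The masking rule covers the surgeon and postoperative manifest refractions. An interim on enrolment, baseline, agreement between biometers or safety complies with it. The settings sentence covers both devices and sits under Surgery. Lens selection before each operation needs powers from both devices, so settings exist on both before that eye has a day-30 refraction. No passage provides for changing them later.

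**The case for a change.** The strongest case for acting is that lens settings are an input to the only primary endpoint and that recording them would cost a few sentences and one table. Masking is stated for the surgeon and the optometrist, but not for whoever holds the settings or runs the back-calculation. If the settings are not recorded before refractions accrue, the sponsor cannot later show from the protocol alone that they were fixed. With a real offset of 0.2 or 0.3 D and Argos truly near the margin, the effect on the error rate would be material.

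Much of this stands. The documentation is thin, and the wording alone does not prove a lock. But the harm requires someone to change one device's settings after seeing outcomes, which the plan does not provide for and which does not sit with settings described as optimized for both. It also requires a sizeable offset in settings already called optimized, and a true difference far from the zero that the sample-size section expects. The interim line adds little: it could only bring such a step forward, and the masking rule neither causes nor prevents it.

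**Conclusion.** No change follows. Followed as written, the plan gives a sound comparison. Refractions stay from the surgeon until the study ends, an interim talk that respects this is possible, and both devices' predictions use settings already in service when lenses are chosen. What is missing is detail that analysts would ordinarily fill by keeping a record of the settings used and applying them throughout.

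In the likelier case of a small offset, the size is 3% to 5% of the margin, and power at the planned difference moves from 90.2% to 92.2%. Larger effects need offsets of 0.2 D or more. All these sizes rest on assumed offsets, assumed error SDs and normal errors. The margin-case percentages computed with a 0.5 D paired SD should not be relied on. The conclusion rests on reading the settings as fixed before surgery and common in principle to both devices, which the text implies but does not state. N = 68 is unaffected.
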